3. BACKGROUND

a. Past Experimental and/or Clinical Findings

Type 2 diabetes (T2D) is a chronic condition which affects the way the body regulates and uses glucose as a fuel, resulting in excess blood glucose levels, which contributes to disorders of the circulatory, nervous and immune systems. T2D affects approximately 415 million people

globally; an estimated 642 million will be affected by 2040 (International Diabetes Federation, 2015). T2D is the leading cause of end-stage renal failure, adult-onset blindness, and nontraumatic amputations, and markedly increases risk for cardiovascular morbidity and mortality (World Health Organization, 2010), resulting in a significant burden on individuals and the healthcare system (Li, Qu, Zhang, et al. 2015).

Three randomized trials have now confirmed that lifestyle modification interventions, which teach lifestyle modifications that reduce excess body weight can significantly reduce progression to T2D among individuals with prediabetes (Pan, Li, Hu, et al, 1997; Tuomilehto, Lindstrom, Eriksson, et al, 2001; Diabetes Prevention Program Research Group, 2002). However, these interventions were very intensive, often requiring over 40 hours of individual counseling and coaching delivered over 1- to 2-year periods. Such intensive interventions, particularly when delivered on an individual basis, are extremely difficult to broadly implement (Damschroder & Hagedorn, 2011). A briefer intervention that would be less expensive to deliver would be much easier to implement on a broad enough scale to reduce the population prevalence of T2D. For instance, we have been able to implement a brief 4-hour eating disorder prevention program to over 6 million adolescent girls in 140 countries to date (Stice et al., 2021).

Fortunately, our research team created a brief obesity prevention program that has produced a 42% to 53% reduction in future onset of overweight/obesity in three randomized controlled trials (Stice et al., 2008; 2014; 2020). The 3-hour Healthy Weight obesity prevention program produced a statistically significant 53% reduction in overweight or obesity onset over 3-year follow-up versus assessment-only controls for adolescent girls and young women with body image concerns and produced.

b. Findings from Past Animal Experiments

N/A

4. RADIOISOTOPES OR RADIATION MACHINES

a. Standard of Care (SOC) Procedures

Identify Week/Month of Study	Name of Exam	Identify if SOC or Research
<Enter text or "NA">	<Enter text or "NA">	<Enter text or "NA">

b. Radioisotopes

i. Radionuclide(s) and chemical form(s)

N/A

ii. Total number of times the radioisotope and activity will be administered (mCi) and the route of administration for a typical study participant

N/A

iii. If not FDA approved: dosimetry information and source documents (package insert, Medical Internal Radiation Dose [MIRD] calculation, and peer reviewed literature)

N/A

c. Radiation Machines – Diagnostic Procedures

- i. Examination description (well-established procedures)
N/A
- ii. Total number of times each procedure will be performed (typical study participant)
N/A
- iii. Setup and techniques to support dose modeling
N/A
- iv. FDA status of the machine and information on dose modeling (if procedure is not well-established)
N/A

d. Radiation Machines – Therapeutic Procedures

- i. Area treated, dose per fraction/number of fractions, performed as part of normal clinical management or due to research participation (well-established procedures)
N/A
FDA status of the machine, basis for dosimetry, area treated, dose per fraction and
N/A
- ii. Source: eProtocol Section 4d (box 2)

5. DEVICES USED IN THE STUDY

a. Investigational Devices (Including Commercial Devices Used Off-Label)

Investigational Device 1	
Name:	N/A
Description:	N/A
Significant Risk? (Y/N)	N/A
Rationale for Non-Significant Risk	N/A
Investigational Device 2	
Name:	N/A
Description:	N/A
Significant Risk? (Y/N)	N/A
Rationale for Non-Significant Risk	N/A
Investigational Device 3	
Name:	N/A
Description:	N/A
Significant Risk? (Y/N)	N/A
Rationale for Non-Significant Risk	N/A

b. IDE-Exempt Devices

IND-Exempt Device 1	
Name:	N/A
Description:	N/A

IND-Exempt Device 2	
Name:	N/A
Description:	N/A
IND-Exempt Device 3	
Name:	N/A
Description:	N/A

6. DRUGS, BIOLOGICS, REAGENTS, OR CHEMICALS USED IN THE STUDY

a. Investigational Drugs, Biologics, Reagents, or Chemicals

Investigational Product 1	
Name:	N/A
Dosage:	N/A
Administration Route:	N/A
Investigational Product 2	
Name:	N/A
Dosage:	N/A
Administration Route:	N/A
Investigational Product 3	
Name:	N/A
Dosage:	N/A
Administration Route:	N/A

b. Commercial Drugs, Biologics, Reagents, or Chemicals

Commercial Product 1	
Name:	N/A
Dosage:	N/A
Administration Route	N/A
New and different use? (Y/N)	N/A
Commercial Product 2	
Name:	N/A
Dosage:	N/A
Administration Route	N/A
New and different use? (Y/N)	N/A
Commercial Product 3	
Name:	N/A
Dosage:	N/A
Administration Route	N/A
New and different use? (Y/N)	N/A

7. DISINFECTION PROCEDURES FOR MEDICAL EQUIPMENT USED ON BOTH HUMANS AND ANIMALS

N/A

8. PARTICIPANT POPULATION

a. Planned Enrollment

- (i) All subjects will be enrolled at Stanford. We expect to enroll 62 participants.
- (ii) N/A
- (iii) Participants are overweight adults (BMI between 25 and 40 kg/m²) between 18-65 years old who have been diagnosed with prediabetes, defined as having elevated HbA1c (5.7-

6.4%). As this is the first test of an adapted Project Health for individuals with Type 2 Diabetes, recruiting a sample that will most likely benefit from it is important in testing its effectiveness.

b. Age, Gender, and Ethnic Background

All participants will be 18-65 year-olds. All ethnicities and genders will be recruited and included.

c. Vulnerable Populations

This study will only enroll adults. All individuals will be consenting on behalf of themselves. We are not specifically recruiting from vulnerable populations, although as long as they meet eligibility criteria then they will be able to participate in the study. We are not specifically recruiting students or employees, but if they are interested in participating, they will not be excluded. The consent form notes the voluntary nature of their participation and that they will not lose any benefit or medical care that they are otherwise entitled for withdrawing from the study.

d. Rationale for Exclusion of Certain Populations

Children are not included as Type 2 Diabetes is not common among children.

e. Stanford Populations

Stanford students, employees, and laboratory personnel may be eligible to participate in this research study. We cannot estimate how many that might be. If any such participants are enrolled, they will go through the informed consent process as any other participant would and receive payment for their participation.

f. Healthy Volunteers

N/A

g. Recruitment Details

Recruitment will take place using both online and in person strategies. Online - Ads will be posted on the internet using social media sites: Twitter, Facebook, and Instagram, community forums: Craigslist and Reddit, and the study website. We will manage an Instagram and Facebook page with postings about the study using the approved images and captions. All posts on the page will be moderated by the research team and set to block commenting or posting by the public. Posting of online ads will be managed based on inclusion criteria, i.e. within the area of the sites, age, etc. If not possible to post within the geographic area we are recruiting (such as on Reddit), then we will specify within post that potential participants must live near the Bay Area. The Social media recruitment posts will be set up such that the security settings do not allow participants or others from the public to post on the wall/public forum. If this is not possible due to the social media platform's settings, the social media posts

will be monitored and any disclosures of PHI removed.

Additionally, all participants who call the Stanford or associated clinics for services are asked about their willingness to be contacted for research. We will put flyers in the community as well as send postcards via email. We will also be able to recruit at clinics around the Bay Area.

Potential participants will also be contacted through our endocrine and IRB approved patient recruitment lists, including the Stanford Diabetes Research Center's clinical registry (in which subjects have already consented to be recruited for research studies). Stanford Diabetes Research Center's clinical registry is composed of individuals who have expressed interest in participating in research and have voluntarily included their name in the registry to be contacted for potential participation in studies. More information on the SDRC registry can be found at: <https://sdrc.stanford.edu/clinical-research-registry>.

Participants will also be recruited through online flyers sent out through established diabetes-related listervs run by diabetes organizations.

The IRB-approved recruitment flyer and email will also be circulated through online websites, forums newsletters, emails listervs, and social media pages (primarily run by diabetes organizations such as DYF and JDRF) and shared with diabetes providers and clinics within and outside of Stanford.

We are also going to use Researchmatch.org.

In addition, we will partner with the Research Participant Engagement Program (RPEP) team for Honest Broker outreach. Potential participants are identified via STARR and invited by RPEP team (honest broker) on behalf of study team. See Section 16 for Honest Broker study invitation letters. We will be using Direct Email / SHC Epic MyHealth / Postal Mail honest broker outreach. For Direct Email, RPEP team provides (via secure Box folder) contact info from interested participants to study team. For Epic MyHealth, study team receives only the interested responses via Epic MyHealth InBasket. For Postal Mail, study team may support the process by sticking pre-printed address labels (created by RPEP, the honest broker) on the envelopes. Invitations will not be sent to the same individual via more than one honest broker outreach method, unless as a separate reminder. The study team will respond to the patient via MyHealth thanking them for their interest, ask them to set up a time to talk on the phone, obtain verbal consent before questions are asked over the phone, and then send our screening survey link that includes a consent and HIPAA Authorization, and confirm their availability for an initial visit.

h. Eligibility Criteria

i. Inclusion Criteria

- (1) 18-65 years of age
- (2) BMI (kg/m²) ≥ 25 or ≥ 23 for Asian Americans
- (4) high-risk prediabetes, defined as 1 of 3 criteria: (1) FPG value = 110-125 mg/dL,

- (2) HbA1c value = 6.0-6.4%, or (3) both FPG 100-109 and HbA1c 5.7-5.9%
- (3) ability to read and speak English at an 8th grade level (to complete assessments and potentially participate in the group intervention)

ii. Exclusion Criteria

- (1) a medically confirmed diagnosis of type 1 diabetes,
- (2) use of anti-hyperglycemic medications (e.g., Metformin) or weight-loss medications
- (3) having a medical condition that would interfere with engagement in a behavior change program (e.g., cancer)
- (4) pregnancy

i. Screening Procedures

Participants will indicate interest by completing a short survey on a secured platform, such as REDCap, that asks them for contact information. From there, a member of the research team will contact them to conduct the telephone screening where verbal consent will be obtained. Prior to the phone screen, the research team will send the potential participant the consent to review before going through it with the research team.

j. Participation in Multiple Protocols

As a part of the informed consent process, subjects will be asked if they are participating in any other research projects. Their participation in other protocols will not exclude them from participation in this study.

k. Payments to Participants

Participants will be eligible to earn up to \$150 for completion of all study activities. \$25 will be awarded per completion of each assessment and blood testing (pre-test, post-test, 3-month) and then an additional \$25 if all assessments are completed. With a \$10 gift card for 1-year follow-up.

- (1) baseline = \$25
- (2) baseline blood tests = \$25
- (3) post-test = \$25
- (4) 3 month follow-up = \$25
- (5) 3-month follow-up blood test = \$25
- (6) completion of all the previous five = \$25
- (7) 1-year follow-up blood test = \$10 Amazon gift card

l. Costs to Participants

There will be no cost to participants.

m. Planned Duration of the Study

It is estimated that the study will take one year. The screening is expected to take 10-15 minutes. Active participation will last about 4 months. Participants will complete the baseline assessment (1.5 hours) and collect HbA1c levels, then complete the six-week intervention (each session is one hour), and then a post-test assessment (about 1.5 hours) and HbA1c. After the initial baseline assessment and the post-test, participants will have completed all necessary tasks until the 3-month follow-up where they will complete the same tasks as the baseline and post-test assessments. While the groups are running, data analysis on baseline data will begin. Once we have complete data for posttest and 3-month follow-up, we will conduct data analysis on the outcome measures. We propose to collect A1c data over 1 year follow up.

First we will check to see in Epic if the participant is a Stanford patient. If they haven't had a recent test or not in Stanford system we will ask if they would be willing to send any recent A1c blood test results. If no to both, the participant will be offered to have an HbA1c kit sent to them to do a finger prick at home and send it to a lab in Minnesota to be processed.

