1. PURPOSE OF THE STUDY

a. Brief Summary

This study aims to test the effectiveness of a Type 2 Diabetes (T2D) prevention program for individuals who have been diagnosed with prediabetes compared to a T2D educational control group. Project Health is an obesity prevention program and has produced a 42% to 53% reduction in future onset of overweight/obesity and also produced greater reductions in negative affect compared to assessment-only controls that persisted. Project Health has been adapted to prevent onset of T2D among individuals with prediabetes. The study aims to test the effectiveness of Project Health at reducing BMI, HbA1c levels, increase physical activity and improve glucose control.

b. Objectives

Aim 1 is to test the hypothesis that participants who complete the T2D Project Health will show significantly greater reductions in BMI and HbA1c, the primary outcomes, by 3-month follow-up than participants randomized to the T2D education video control condition.

Aim 2 is to test the hypothesis that participants who complete the T2D Project Health will show significantly greater reductions in self-reported caloric intake and greater increases in physical activity by 3-month follow-up than participants randomized to the T2D education video control condition.

If this pilot and feasibility trial provides evidence that Project Health significantly reduces weight gain and improves glucose control, we plan on conducting a fully-power trial that will test whether this brief, cost effective prevention program significantly reduces future onset of T2D among individuals with impaired glucose control. As such, this represents a translational study on the prevention of T2D.

c. Rationale for Research in Humans

The purpose of this study is to test the effectiveness of a Type 2 Diabetes prevention program, adapted Project Health. This study must use humans due to the nature of the educational aspect because the programs require speech as a method of communication.

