2. STUDY PROCEDURES

a. Procedures

Participants will be recruited through flyers, online postings, and other postings at various clinics in the Bay Area. To determine eligibility, during screening participants will be asked their age, gender.

On the flyers and other recruitment materials, participants will be directed to a short survey on a secure platform that only asks for contact information to show interest in the study. The study team will use the contact information provided to set-up a phone screen for interested individuals. If the participant shows interest through one of the Honest Broker methods (such as MyChart) or through ResearchMatch.org which shares the contact information with the research team, then a member of the research team will reach out to the individual using the contact information provided to thank them for their interest and schedule a phone screen. See section 13 for the phone screen.

After the participant completes the phone screen, a member of the study team will contact them to confirm eligibility. Consent (for ages 18- 65) will be secured prior to enrollment.

Baseline Assessment:

After eligibility is confirmed but before groups begin, the participant will come in for their baseline assessment. At baseline, participants will complete the Paffenbarger Activity Questionnaire to assess physical activity, the Beck Depression Inventory, and the Eating Disorder Diagnostic Scale. We will also have participants get an HbA1c test and fasting glucose test through the Stanford CTRU. Finally, participants will complete a Bod Pod Assessment, measuring Body Fat. Prior to the start of groups, participants will complete the Automated Self-Administered 24-hr Dietary Recall (ASA-24) to assess dietary intake on 2 weekdays and 1 weekend.

Prevention program:

After baseline assessments are completed, participants will be randomized to either the Project Health groups or the educational control.

Randomization:

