If participants are randomized to Project Health, they will meet in groups of 6 individuals led by clinician. Groups will meet once a week in-person for an hour, for six weeks. Each week involves homework that participants are asked to complete before the next session. If participants are assigned to the Education intervention, they will be asked to watch one-hour of videos including information about T2D each week for six weeks.

Post-Test:

After the six weeks of either Project Health or the educational control, participants will be asked to complete the same assessments that they did at baseline, but not the blood tests.

3-Month Follow-up:

At 3-month follow-up, participants will again complete the assessments. After the 3-month follow-up, participants have completed all study responsibilities.

1-Year Follow-Up:

We propose to collect A1c data over 1 year follow up

First we will check to see in Epic if the participant is a Stanford patient.

If they haven't had a recent test or not in Stanford system we will ask if they would be willing to send any recent A1c blood test results.

If no to both, the participant will be offered to have an HbA1c kit sent to them to do a finger prick at home. The participant will send the kit to the research lab in Minnesota to be processed. Kits come with already pre-paid shipping labels that are addressed only to the Minnesota lab, no return address or any PHI from the participant is included. The participant will be offered a \$10 Amazon gift card for completing and shipping the HbA1c kit.

b. Procedure Risks

These research procedures provide minimal risk to subjects. We are using current and empirically evaluated measures and research staff available who have been fully trained both in administrating physiological interviews. Project Health has also been tested in

multiple trials and has produced only positive effects, there has been no history of symptoms worsening as a result of participating in the program.

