Evaluating a Type 2 Diabetes Prevention Program

NCT: 5822648

04/16/2023

**Analyses.** For the continuous response variables in Aims 1 and 2 we will fit linear mixed effects models (LME) or generalized additive models (GAM) if change across the study is nonlinear. All models will include an interaction of time since the start of the study (in months) and condition (as well as all lower-order main effects). For both LMEs and GAMs, we will control for the lack of independence between the observations within a participant by including random intercepts and random slopes (if necessary) for the participants in our models and for participants nested within groups.

To detect for differences in the onset of T2D (Aim 1) between the intervention and control condition, we will fit a Cox proportional hazard model using the survival package (Therneau, 2022) in R. The proportional hazard assumption will be assessed and in the event of violations of this assumption, stratified proportional hazard models will be fit.

For the mediation analysis for Aim 2, the mediation package (Tingley et al., 2014) in R will be used to employ the causal mediation approach described in Imai et al. (2010). This is a more general and flexible causal mediation framework than the traditional structural equation modeling approach to mediation. Specifically, this approach enables (1) definitions of causal mediation effects that are independent of a particular statistical model, (2) specification of the identifiability assumption, and (3) a framework that can be applied to a myriad of models (most importantly for this study, LMEs, GAMs, and survival models). In addition, sensitivity analyses can be conducted to explore the sequential ignorability assumption. Using this framework involves modeling the onset of T2D via a parametric survival regression model that includes condition and the proposed mediator (percent body fat). This model's output is then combined with the mediator model's output, the percent body fat model from Aim 1, and used to calculate the average causal mediation effect (ACME), the proportion of the total effect that is mediated as well as other mediation statistics, which can then be tested using either quasi-Bayesian Monte Carlo or the non-parametric bootstrap.

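### The protocol gives two answers on whether HbA1c is drawn at post-test; if it is not, the SAP's optional random slopes and nonlinear terms cannot be estimated for HbA1c through 3 months, and the SAP does not name the visits that enter the model

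*Protocol*

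**What the plan says.** Protocol section 1b makes HbA1c one of two primary outcomes: Aim 1 looks for "significantly greater reductions in BMI and HbA1c, the primary outcomes, by 3-month follow-up". Section 2a sets the first measurement: "We will also have participants get an HbA1c test and fasting glucose test through the Stanford CTRU".

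The sections part ways at post-test:

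- Section 2a, Post-Test, has participants "complete the same assessments that they did at baseline, but not the blood tests".
- Section 8m, going through the same visits, follows the six-week intervention with "and then a post-test assessment (about 1.5 hours) and HbA1c".
- Section 8k awards $25 per "completion of each assessment and blood testing (pre-test, post-test, 3-month". It then itemises the payments. The only $25 blood-test items are the one at baseline and the "3-month follow-up blood test". The stated maximum is $150, with a separate $10 gift card for the 1-year test.

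Sections 2a and 8m also propose a 1-year HbA1c. It would come from the medical record, from results the participant sends in, or from a home finger-prick kit.

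The SAP uses one model family for all continuous outcomes in Aims 1 and 2. This is a linear mixed model with time in months by condition, or a generalized additive model (GAM) if change is nonlinear. Repeated measures are handled by "including random intercepts and random slopes (if necessary) for the participants in our models", with a further term for participants nested within groups. The SAP does not list the visits that enter the model for any outcome.

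**The concern.** Sections 2a and 8m cannot both be followed. HbA1c is a blood test in this protocol, so no reading of the 2a exclusion lets the 8m statement stand. A sample not taken at the end of the six weeks cannot be obtained later.

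The number of HbA1c values per participant also decides which of the SAP's model options are available for this outcome. With the visits unstated, two choices on a primary outcome stay open until the data are in hand: whether a random slope or a smooth term is attempted, and whether the 1-year value is included.

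**Working it through.** **1. Payments.** This is the only stated figure that bears on the schedule. Six items at $25 (baseline, baseline blood, post-test, 3-month, 3-month blood, completion of all five) give 6 x $25 = $150, which reproduces the stated maximum. A post-test blood item at the same rate would give 7 x $25 = $175. The list and its total therefore match section 2a.

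**2. Visit times (assumed).** Baseline is 0 and post-test is about 1.5 months (six weeks). The 3-month visit is about 4.5 months if counted from post-test, and the 1-year value is at about 12 months. Counting the 3 months from baseline, so that the visits are at 0 and 3, gives the same ranks below.

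**3. Random slope from two values.** Let a be the intercept variance, b the slope variance, c their covariance and s the residual variance. With visits at 0 and t:

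- variance at baseline = a + s
- covariance = a + tc
- variance at t = a + 2tc + t²b + s

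That is 3 equations in 4 unknowns. Raise s by d, lower a by d, raise c by d/t and lower b by 2d/t². The three changes are then:

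- −d + d = 0
- −d + d = 0
- −d + 2d − 2d + d = 0

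The data cannot tell these parameter sets apart. A numerical rank check agrees: rank 3 for 4 parameters.

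**4. Curvature from two values.** A quadratic in time needs 3 coefficients per arm, and two visits supply 2 means per arm. The rank is 2 of 3.

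**5. Random intercept from two values.** Only a and s are needed, against 3 covariance elements, so the model is identified. With complete data, the time by condition coefficient times t equals the between-group difference in mean change.

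**6. A third value.** With visits at 0, 1.5 and 4.5 months there are 6 covariance elements, rank 4 for 4 parameters, and quadratic rank 3 of 3. Visits at 0, 4.5 and 12 months give the same ranks.

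**7. Illustrative fits.** One simulated data set was used per visit pattern, with n = 62. The assumed SDs were 0.2 (intercept), 0.02 per month (slope) and 0.1 (residual); none comes from the documents.

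- Two visits: the random-intercept model converged (interaction −0.0176 per month, SE 0.0102). The random-slope model did not converge.
- Adding a complete 1-year value: the random-slope model converged.
- With an assumed 40% missing at 1 year: it did not converge.

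**8. Precision of the two-visit analyses.** Assume equal variance at both visits and within-arm correlation ρ. The variance of the difference in mean change is proportional to 2(1 − ρ). That of the baseline-adjusted difference is proportional to 1 − ρ². The ratio of the second to the first is (1 + ρ)/2, which is below 1 for any ρ below 1. The two-visit random-intercept fit gives ρ = 0.03317/(0.03317 + 0.01645) = 0.668, so the ratio is 0.834. The value of ρ is illustrative only.

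**The case against.** A reader might infer that the primary HbA1c analysis cannot be run without a post-test draw. The documents do not support that. The SAP adds random slopes only where necessary and uses a GAM only if change is nonlinear. Its base model fits two visits and tests the Aim 1 contrast. This objection stands in full: what is lost is two optional extensions.

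The 1-year HbA1c is a third time point, so it would also be wrong to say that these terms can never be estimated for HbA1c. That stands in principle, but the support is weak. The value is optional, comes from mixed sources and has no fixed date. It lies beyond the endpoint, so it shows nothing about the shape of change before 3 months. Put into a linear time by condition model, it would turn the slope into change over about a year. Scatter in actual visit dates (assumed SD 0.3 month) also restores formal rank with two visits, but identification then rests on that scatter alone.

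The payment sentence might be read as a second contradiction. The list directly beneath it resolves the ambiguity, so the real conflict is between 2a and 8m.

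Finally, it is conjecture that staff would in fact collect different data. The documents show only that the instructions conflict. The 3-month blood test appears in the payment list, so only an intermediate value is in doubt.

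**Conclusion.** The contradiction between 2a and 8m over the schedule of a primary outcome is real and needs correcting. The itemised payments and their $150 total fit a schedule with no post-test draw.

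On that schedule, random slopes (3 covariance elements for 4 parameters) and nonlinear change (rank 2 of 3) cannot be estimated for HbA1c through the 3-month endpoint. This holds for visits at common nominal times and without the 1-year value. The random-intercept model is unaffected. The SAP's remaining gap is that it does not say which HbA1c visits enter the model, the 1-year value included.

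This is an internal inconsistency that wording can fix. The 3-month primary comparison is possible under either reading, so the point should be corrected but does not put the trial's main analysis at risk. The identifiability result is algebraic and depends on no variance, power or sample-size figure. The simulated fits only illustrate it.

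**What to change.** Reconcile protocol sections 2a, 8k and 8m so that all three give one HbA1c schedule, and reword the 8k payment sentence to match its own list.

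If there is no post-test draw, add to the SAP that:

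- the primary HbA1c analysis is the baseline-adjusted between-group difference at 3 months, keeping the planned allowance for group clustering;
- random slopes and GAMs are limited to outcomes measured at all three visits;
- the 1-year HbA1c is analysed separately and stays out of the 3-month primary contrast.

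The baseline-adjusted analysis uses a value already collected and is more precise than the unadjusted two-visit contrast.

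If the draw is kept, add it to 2a and to the payment list, and still state how the 1-year value is handled.

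With no draw, the cost is a few sentences. With a draw paid at the same rate, the maximum becomes $175 and payments rise by up to 62 x $25 = $1,550. Laboratory costs would be extra, and the documents do not give them.
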